6.7. Efficacy Figures

Figures will be presented for IGA and PGA success rate by visit using observed data. The week 12 success rate using the same MAR multiple imputation method as used in the primary analysis will also be graphed.

Figures will also be presented for the success rate at week 12 for each subgroup using MAR multiple imputation.

6.8. Efficacy Subgroup Analysis

The subgroup analyses will repeat the analysis of the three co-primary and co-secondary endpoints on all subgroups. The MAR multiple imputation method will be used to handle missing data.

For lesion count subgroup analysis, the t-tests will be done assuming unequal variances using Satterthwaite's formula for variance.

6.9. Dermatology Life Quality Index

Descriptive statistics treating the (C)DLQI totals scores as a continuous measure will be presented with observed and change from baseline summaries. Counts and percentages of subjects within categorized ranges ("No effect" to "Extremely large effect") will also be presented. These summaries will be presented for the DLQI and CDLQI.

Total score is calculated assigning a numerical equivalent to each answer, and summing them across the 10 questions. Answers are scored as follows:

- Very much: 3
- A lot/Quite a lot: 2
- A little/Only a little: 1
- Not at all: 0

For question 7, answering a "Yes" scores as 3 and a "No" scores as 0, however answering "No" requires answering question 7b where "A lot," "A little," and "Not at all" as scored as normal.

Descriptive statistics treating the (C)DLQI dimensional scores as a continuous measure will also be presented with observed and change from baseline summaries. These will be presented for DLQI and CDLQI separately.

For the DLQI, dimensional scores will be calculated using the following questions:

- Symptoms and Feelings: questions 1 and 2
- Daily Activities: questions 3 and 4
- Leisure: questions 5 and 6
- Work and School: question 7
- Personal Relationships: questions 8 and 9
- Treatment: question 10

For the CDLQI, dimensions cores will be calculated using the following questions:

- Symptoms and Feelings: questions 1 and 2
- Sleep: question 9
- Leisure: questions 4, 5, and 6
- School or Holidays: question 7
- Personal Relationships: questions 3 and 8
- Treatment: question 10

7. Safety Analyses

7.1. Drug Exposure

Study and Treatment Duration

Study duration will count the number of days a subject is on the study, regardless of their treatment requirements. It is calculated as study end date minus study start date plus one.

Subjects are expected to take one application per day on the study. Treatment duration for the face will be calculated as the subject's treatment end date minus treatment start date plus one; treatment duration on the trunk will be calculated as the subject's treatment end date minus treatment start date plus one.

Total Applications

Applications taken is not collected on the CRF, so to estimate the number of applications a subject took, the number of recorded missed doses will be subtracted from the number of doses the subject should have taken to arrive at the number of taken applications.

Subjects who have visits after their treatment end date record the time between in one of two different ways:

1. Some record a number of missed doses between treatment end and their current visit. These do not count as actual missed doses, as the subject was off treatment.
2. Others record "NA" or leave it missing.

Thus, the calculation of total applications on the face will be done in the following steps:

1. Start with the subject's treatment start date.
2. Chose an end date to use to calculate the starting number of doses measured on the CRF. If the subject has a non-missing recorded number of missed doses at any date after their treatment end date, use the latest date available with missed doses recorded. Otherwise, use treatment end date.
3. Calculate the starting number of doses as end date minus treatment start date plus 1.
4. From that, the total number of all missed doses on the face will be subtracted.

The calculation of total applications on the trunk will be done following the same steps, but using PGA scores and counts of missing doses on the trunk.

Expected Applications

A subject's expected number of applications will assume that subjects take one application per day of treatment duration. Thus, a subject's expected applications is equal to their treatment duration.

Compliance

Compliance percentage will be calculated as a subject's total applications divided by their expected applications multiplied by 100.

7.2. Medication Usage

A subject's average daily medication usage (g/day) will be calculated as their total medication usage divided by their overall treatment duration. Overall treatment duration is calculated as the subject's treatment end date minus their treatment start date plus one.

As per Galderma's clinical supply process, the weight of each dispensed tube is assigned based on the average weight of a sample of kits from each batch. Hence, it is possible that some subjects are recorded as having returned more grams of drug than they were dispensed. If a subject's total medication usage is negative, it will be set to zero.

7.3. Adverse Events

A treatment-emergent adverse event is defined as an adverse event that occurred, or increased in severity, on or after the date of the first dose of study drug. Events with missing severity will be considered severe; events with missing relatedness data will be considered related to the study drug.

Adverse events of special interest will be summarized, and are defined as follows:

- Out-of-range laboratory results that are identified as clinically significant and related to the study drug;
- Related cutaneous AEs which lead to permanent treatment discontinuation, and
- Suspicion of allergic reaction suspected to be related to the study drug.

Severe adverse events are defined as those with severity marked as "Severe" on the CRF. Adverse events related to study drug or protocol procedure are defined as those marked as having a "reasonable possibility" of being related to study drug or protocol procedure, respectively, on the CRF.

A listing of pre-treatment adverse events will be included. Pre-treatment adverse events are those with an onset date prior to the date of the first application of study drug.

7.4. Local Tolerability

Local tolerability will be summarized by visit on the face and trunk separately. Summaries will present descriptive statistics of local tolerability scores when treated as a continuous measure, as well as counts and percentages of subjects with each score treated as categorical. Categorical summaries of scores that are worsened from baseline will also be presented.

Worsened from baseline is defined as having a local tolerability assessment at the summarized time point that is greater than the local tolerability assessment at baseline.

Subgroup analysis of local tolerability scores will be presented separately for the face and trunk. These summaries will treat the scores as categorical, and will present scores that have worsened from baseline for both the final and worst scores per subject.

Local tolerability scores will also be presented treating the score as dichotomous. Subjects will be summarized into two categories based on their score: "None (0)" or "Mild/Moderate/Severe (1-3)," and presented at Baseline, Final visit, and their Worst score.

Graphical assessment of local tolerability will be done on all subjects, not just those with a local tolerability assessment worsened from baseline. Subgroup analysis of local tolerability will not be graphed.

7.5. Laboratory Values

Laboratory values will be presented using the International System of Units (SI units).

For summary purposes, laboratory values that are listed as above or below particular thresholds will be numerically listed as above or below that threshold, respectively, by the minimum measured amount for that parameter. For example, if a parameter is measured to two decimal places, and has a result of "> 5" then, for summary purposes, the value of 5.01 will be used. Values with "<" or ">" will be classified as Low or High, respectively, unless such classifications aren't applicable for that parameter, in which case they will be classified as Normal.

Shifts in laboratory assessments will be presented from the baseline visit to the last post-baseline visit; subjects missing baseline or post-baseline laboratory data will not be included.

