7.5.4 Laboratory parameters

A summary table of the categorical grade shift changes using the normal ranges from baseline to Week 12/ET will be presented for each treatment group by each laboratory category parameter using the SAF population.

Only subjects with both baseline and Week 12/ET assessments will be included in this analysis.

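### Laboratory results reported with `<` or `>` are classed Low or High from the sign alone, so a reporting limit inside the normal range yields an abnormal class, and possibly a shift, that the result does not support

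*SAP*

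**What the plan says.** SAP 7.5.4 (Laboratory parameters) describes a table of "categorical grade shift changes using the normal ranges from baseline to Week 12/ET". Low, Normal and High there are set by the normal range.

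Addendum 7.5 (Laboratory Values) adds two conventions for results reported only as beyond a threshold:

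- **A number.** Such results "will be numerically listed as above or below that threshold, respectively, by the minimum measured amount for that parameter". In the addendum's example, for a result of `> 5` measured to two decimals, "for summary purposes, the value of 5.01 will be used".
- **A class.** They "will be classified as Low or High, respectively", except where those classes do not apply to the parameter, "in which case they will be classified as Normal".

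The class is tied to the sign. Nothing says that the threshold or the substituted number is compared with the normal range. The addendum also sets the comparison: "Shifts in laboratory assessments will be presented from the baseline visit to the last post-baseline visit". Its Purpose section says that it prevails over the SAP where the two differ, so the sign rule governs the table.

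**The concern.** A reporting limit and a limit of normal are different quantities. A `<` sign says that the value is below what was reported as measurable, not that it is below normal. Under the addendum, one shift table uses two definitions of abnormal: the normal range for ordinary numeric results and the sign for censored ones.

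The exception removes the problem only where Low or High does not apply. It does not reach a parameter with both classes whose reporting limit lies inside the range. It is also worded for the parameter as a whole, so the handling of `<` is unclear where only High is meaningful.

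At stake is the accuracy of the shift table. Change from baseline in laboratory tests is a listed safety endpoint (SAP 4.2). The protocol's schedule of assessments plans laboratory tests only at Screening and at Week 12/ET, so one mislabelled result can decide a subject's cell.

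**Working it through.** **1. The plan's own figure.** For `> 5` at two decimals, the substituted value is threshold + smallest unit = 5 + 0.01 = 5.01. This matches the addendum.

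**2. Sign against range.** The documents give no normal ranges or reporting limits, so every range below is an assumption, as are all the results other than `> 5`. For a `<` result the substituted value is threshold − 0.01 (5 − 0.01 = 4.99; 3 − 0.01 = 2.99).

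| Result | Assumed range | Substituted value | Class by sign | Substituted value against range | What the result establishes |
|---|---|---|---|---|---|
| `> 5` | 1 to 10 | 5.01 | High | Normal | Normal or High, not known which |
| `> 5` | 1 to 5 | 5.01 | High | High | High |
| `< 5` | 3 to 21 | 4.99 | Low | Normal | Normal or Low, not known which |
| `< 3` | 3 to 21 | 2.99 | Low | Low | Low |
| `< 5` | 0 to 21 | 4.99 | Low, unless the exception is read by direction | Normal | Normal, if values cannot be negative |

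The sign rule is right in rows 2 and 4, where the reporting limit coincides with the limit of normal. It is unsupported in rows 1 and 3, where the reporting limit is inside the range. Row 5 depends on how the exception is read.

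**3. From class to shift.** Take a parameter like row 3.

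- Numeric normal at baseline, `<` afterwards: shown as Normal to Low.
- `<` at baseline, numeric normal afterwards: shown as Low to Normal.
- `<` at both visits: shown as Low to Low. The class is unsupported, but there is no shift.

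The first two are false shifts whenever the censored value was in fact normal.

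**4. Illustrative size.** The true count cannot be derived. To show scale for one affected parameter, assume that all values are truly normal and that a share q of results falls between the lower limit of normal and the reporting limit. Assume further that the two visits follow a bivariate normal distribution with correlation ρ, and that all 600 subjects per arm (SAP section 2) have paired results, which is an upper bound. Then

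false Normal-to-Low shifts per arm = 600 × [q − P(both visits below the reporting limit)].

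With ρ = 0 the bracket is q − q².

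| q | ρ = 0 | ρ = 0.8 |
|---|---|---|
| 1% | 600 × 0.0099 = 5.9 | 600 × 0.0062 = 3.7 |
| 5% | 600 × 0.0475 = 28.5 | 600 × 0.0252 = 15.1 |
| 10% | 600 × 0.0900 = 54.0 | 600 × 0.0438 = 26.3 |
| 20% | 600 × 0.1600 = 96.0 | 600 × 0.0710 = 42.6 |

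By symmetry, the false Low-to-Normal count is the same again. If no parameter has a reporting limit inside its range, q = 0 and the count is 0.

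**The case against.** **No affected parameter is shown.** This stands. The documents name only hematology, chemistry and urinalysis. The `> 5` example illustrates numeric substitution, and the upper limit of 10 used with it above is assumed. A reader might infer that the shift table will contain false shifts. The documents support only that the rule permits them.

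**The addendum overrides the SAP openly.** This also stands. A reader might call the two sections an unresolved contradiction, but the addendum's Purpose section settles which prevails. What remains is that the override mixes two bases in one table without stating a reason.

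**Flagging doubtful results matches the addendum's other safety conventions.** Addendum 7.3 treats missing severity as severe and missing relatedness as related. The parallel is fair for a post-baseline result. At baseline the rule is not cautious: a subject with `<` at both visits who truly moved from Normal to Low appears as Low to Low.

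**Comparing the substituted value with the range would err the other way.** This is correct, and it rules out the obvious remedy. With `< 5` and an assumed range of 3 to 21, 4.99 counts as Normal although the true value could be 2. That replaces one unsupported class with another.

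**The consequences are limited.** Agreed. Safety analyses are descriptive (SAP 7.5) and the rule is the same in both arms. A laboratory adverse event of special interest must be identified as clinically significant and drug-related (addendum 7.3), so the sign alone cannot create one.

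**Conclusion.** The point holds in a limited form. Addendum 7.5 departs from the normal-range basis of SAP 7.5.4 by classing censored results from the sign. For a parameter with both Low and High classes and a reporting limit inside the range, it labels as abnormal a result not shown to be abnormal. It can produce a false shift in either direction when only one of the two visits is censored.

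The size is unknown and may be zero. The counts above rest wholly on assumed shares, correlations and complete pairing, and they illustrate scale only. A reader might conclude that every `<` or `>` result is misclassified, or that the laboratory safety findings are unreliable. Neither follows: the rule is right wherever the reporting limit is at or beyond the corresponding limit of normal, and nothing in the documents shows a parameter where it is not. Efficacy is unaffected. This is a minor correction, worth making because it is cheap.

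**What to change.** Amend addendum 7.5 as follows.

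- Class a `<` result as Low only if its reporting limit is at or below the lower limit of normal.
- Class a `>` result as High only if its reporting limit is at or above the upper limit of normal.
- If the reporting limit lies inside the range, do not count the result as Low or High. Show it as within range or indeterminate (censored), with a footnoted count.
- Apply the exception for non-applicable classes separately to Low and to High.

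The numeric substitution can stay for the descriptive statistics.

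The cost is a short change of wording and one extra category or footnote in the shift-table shell. Programming needs the threshold, which is part of the reported result, and the normal ranges, which SAP 7.5.4 already requires. The documents show no dataset specification, so the availability of both should be confirmed. The price in content is that some truly abnormal censored values will not be counted as Low or High; the footnoted count keeps them visible. If no reporting limit lies inside a range, nothing changes for parameters with both limits of normal.

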7.6. Vital Signs

Pulse rate, systolic blood pressure, and diastolic blood pressure will be summarized by visit. Shifts in overall vital sign assessments will be presented from the baseline visit to the last post-baseline visit; subjects with no post-baseline vital sign data will not be included. Shifts in normality classification of vital sign parameters based on normal reference ranges will also be presented.
